### Study Plan

120 female patients planned to receive whole breast radiation (+/- lymphatic drainage) in the radiotherapy unit at Sheba, who give written consent for participation, will be entered into the study and randomized. Based on statistical evaluation, 65 will receive the aloe Vera and 55 will receive the HA Gelronate® in blinded packages.

Patients will undergo CT simulation with 3D treatment planning (as routinely done) and will receive 42.4 Gy in daily fraction of 2.65 Gy, five times per week to the whole breast according to the standard department protocol, with or without concomitant or subsequent lumpectomy cavity boost. Patient data including demographics, staging, systemic therapy, radiation details, other medications will be recorded in the attached forms (Appendix A, pages 7-9 below).

BTG will provide sets of bottles sufficient for treatment of at least 120 patients, plus any extra gel bottles as needed for the participants to complete accrual and full treatment for 120 patients.

The study nurses will provide each patient with the bottle and will ensure that the patient understands how to apply according to protocol. The gel will be applied as a thin lotion twice a day, immediately after radiotherapy treatment and once more in the evening/morning. The therapy should continue for 10 days following the end of radiation therapy.

The study nurses will examine each patient weekly during treatment and 7-10 days after completion of radiotherapy. At each visit skin reaction based on RTOG toxicity score will be recorded and the patient will complete a short questionnaire regarding subjective and objective skin reaction. The patient's skin will be photographed (no face in the picture) on fraction 10-11, 15-16 and at the follow-up visit, days 9-10 after the end of radiation. This will be done with a digital camera and the electronic image will be stored for later evaluation. The images will be stored anonymously except for the patient's study number.

Any patient developing moist desquamation or other grade 3 skin reaction during the radiation will stop treatment and will receive topical therapy as clinically indicated.

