**Background**

One of the dose-limiting effect of radiotherapy is the acute reaction that ionizing radiation induces in normal tissues, i.e. skin. The severity of this acute reaction may link to different parameters, patient associated (BMI, diabetes) and radiation associated (dose per fraction and total dose).

Hyaluronic acid (HA) is linear polysaccharide formed from repetitions of a disaccharide unit composed of one aminosugar and one uronic acid residue ([D-glucuronic acid (1- $\beta$ -3) N-acetyl-D-glucosamine (1- $\beta$ -4)]n) (Figure 1).

Study Protocol V3 7.1.2019

Fig. 1. Disaccharide repeating unit of hyaluronic acid.

The biopolymer is widespread in soft tissues (vitreous humour of the eye, joints, synovial fluid, skin and more). In vertebrates, HA has a wide variety of functions including maintenance of tissue hydration in the skin, sustaining tissue physical properties and induce rate changes in cell proliferation, cell migration and angiogenesis.

There are two industrial methods for the production of HA: from rooster combs or from bacterial fermentation. Bio-Technology General (Israel) Ltd. developed and manufacture HA for ophthalmology and orthopedics purposes. BioLon and BioLon Prime are two products for operations in the interior chamber of the eye (cataract surgeries, cornea implantation etc.) and Euflexxa (Arthrease) syringes are for pain relief in patients suffers from osteoarthritis (OA).

Due to its characteristics and biological properties including wound healing (Primavera et al. 2006, Moore et al 2005, Hanci et al 2015), HA may eliminate or reduce adverse events (AEs) like skin dermatitis. The purpose of this study is to evaluate the capability of 1% HA solution to eliminate or reduce skin reaction during radiation i.e. dermatitis.

The tested product, Gelronate®, is gel composed of 1% high molecular weight pharmaceutical grade sodium hyaluronate and two types of commercial preservatives (Germal 115 and Phanochem/Salinip/Phenonip) dissolved in pharmaceutical grade purified water. Gelronate® supply in an airless pump bottle contain ~30ml gel. The aloe Vera 99.9% product is made by ESI, Israel, with no artificial coloring, in the same package with no identification.

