### **Eligibility:**

#### **Inclusion Criteria:**

1. Female patients aged at least 18 years with unilateral breast cancer following lumpectomy +/- chemotherapy.
2. Planned to receive 42.4 Gy whole breast irradiation +/- boost to tumor bed.
3. ECOG performance status 0-2.
4. Capable of giving written informed consent.
5. No co-morbidities known to affect radiotherapy reactions.
6. No co-existing acute or chronic skin disease.
7. No evidence of infection or inflammation of breast to be treated.

8. Not receiving chemotherapy during radiotherapy course. Biological therapy (e.g. Herceptin) or hormone therapy will be allowed during the study.

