**Statistical Considerations:**

Based on published data and previous experience we expect around 90% of patients to develop some degree of skin reaction and about 20% would require medical intervention due to grade 2-3 skin reactions. (Ben-David et al 2016, Fenig et al., Kodiyan et al. 2015, Olsen et al 2001).

The relative large number of patients in the study was chosen in order to be able to have sufficient amount of data on large variety of patients (different age, BMI, skin color, origin, smokers/non-smokers etc.). Participation in this study will be offered and available to all radiation treated patient in the institute, therefore large variety of patients are expected to participate in this study. As a result, the data that will be obtained in the study may be used by any irradiation institute in the world.

In addition to the weekly nurse/patient evaluation of skin toxicity (see appendix A), at the completion of the study the patient photographs will be evaluated blindly by a panel of 3 radiotherapy staff. The digital photo with the worst reaction of each patient will be scored.

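### Does the unexplained 65:55 sample size, credited to a statistical evaluation the protocol does not show, need correcting?

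*Protocol*

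**What the plan says.** Study Plan sets the size, "120 female patients planned to receive whole breast radiation (+/- lymphatic drainage) in the radiotherapy unit at Sheba", and attributes the split to a calculation: "Based on statistical evaluation, 65 will receive the aloe Vera and 55 will receive the HA" gel.

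Statistical Considerations offers two planning rates, neither tied to an arm. For any reaction it states: "we expect around 90% of patients to develop some degree of skin reaction". For reactions that call for treatment, its figure is different: "about 20% would require medical intervention due to grade 2-3 skin reactions". Its reason for the size is that the number was "chosen in order to be able to have sufficient amount of data on large variety of patients", with age, BMI, skin color, origin and smoking as examples. It adds that every irradiated patient in the institute will be offered participation and that "the data that will be obtained in the study may be used by any irradiation institute in the world".

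The protocol gives no significance level, power, target difference, dropout allowance or reason for unequal arms.

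The Background links severity to factors that are "patient associated (BMI, diabetes) and radiation associated (dose per fraction and total dose"). The Inclusion Criteria limit entry to women after lumpectomy planned for 42.4 Gy and require "No co-morbidities known to affect radiotherapy reactions". The primary endpoint is the development and degree of skin reaction, assessed by RTOG grade, photograph score and patient questionnaire. Reaction needing conventional topical therapy is the secondary endpoint.

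**The concern.** Two sections give different reasons for the same number. One points to a calculation; the section where that calculation should appear offers diversity of patients instead. Two overall rates cannot by themselves produce an unequal split with fewer patients on the test product.

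The protocol also calls the number relatively large and sufficient. If a reader takes that to mean adequate power, a null result could be read as showing no benefit in a large and varied sample, when a halving of the intervention rate would probably have been missed. Comparisons within BMI, smoking or skin-color groups would be weaker still.

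Finally, the claims of open recruitment and worldwide use sit badly with one center, one schedule, lumpectomy patients only, and a criterion that bars co-morbidities affecting skin reactions.

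**Working it through.** **Inputs.** From Study Plan: 65 and 55 patients. From Statistical Considerations: 90% with any reaction and 20% needing intervention. Assumed, because the protocol is silent: two-sided 5% (with one-sided 5% as the range), 80% power (with 90% as the range), and no dropout.

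**Can the stated size be reproduced?** No, because no effect is given. The nearest back-fit is 90% against 70%, which needs 62 per arm (124 in total) at 1:1, or 67:57 at the protocol's ratio. It has 79% power at 65:55. The protocol never states a rate of 70%, so this is not a reproduction.

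**Power on the two stated rates.** With pooled rate p̄ = (65·p1 + 55·p2)/120,

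power = Φ{ [|p1 − p2| − 1.96·√(p̄(1 − p̄)(1/65 + 1/55))] / √(p1(1 − p1)/65 + p2(1 − p2)/55) }.

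- 20% to 10%: p̄ = 0.154; (0.10 − 1.96 × 0.0662)/0.0640 = −0.46; power 0.32.
- 90% to 80%: p̄ = 0.854; (0.10 − 1.96 × 0.0647)/0.0655 = −0.41; power 0.34.

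Solving the same formula for the detectable rate gives:

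| Assumption | From 90% to | From 20% to |
|---|---|---|
| Two-sided 5%, 80% power | 69.8% | 3.5% |
| Two-sided 5%, 90% power | 65.9% | 1.7% |
| One-sided 5%, 80% power | 72.5% | 5.0% |

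**What the 20% refers to.** It is the share needing medical intervention, which corresponds to the secondary endpoint. It is not the incidence of grade 2-3 reactions, for which the protocol gives no figure. The 20% column therefore says nothing direct about the RTOG primary endpoint.

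**Graded analysis.** The primary endpoint includes degree.

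- For a score, the detectable standardized difference at 80% power is (1.96 + 0.84) × √(1/65 + 1/55) = 0.51 SD, and 0.59 SD at 90% power. That is a moderate effect.
- For ordinal grade, the answer depends on a distribution the protocol does not give. At an odds ratio of 0.33, simulated rank-test power is about 0.79 if control grades 0/1/2+ split 10/70/20%. It is about 0.89 if grades 0/1/2/3 split 10/45/35/10%.
- Under the first split, an odds ratio of 0.33 takes 20% to 7.7% (odds 0.25/3 = 0.083) and 90% to 75% (odds 9/3 = 3). Both changes are smaller than the yes/no figures in the table.

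**Precision.** A single 20% rate in 120 patients has a 95% half-width of 1.96 × √(0.16/120) = 7.2 points. The between-arm difference has 1.96 × √(0.16 × (1/65 + 1/55)) = 14.4 points, rising to 14.4/√0.5 = 20 points in a half-sized subgroup and 14.4/√0.2 = 32 points in a one-fifth subgroup.

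**Cost of the split.** Efficiency relative to 60:60 is 4 × 65 × 55/120² = 0.993, a loss of 0.7%.

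**Variety against eligibility.** The factors named in Statistical Considerations are age, BMI, skin color, origin and smoking. Beyond the minimum age of 18, no criterion expressly restricts any of them. The co-morbidity criterion names neither BMI nor diabetes, and diabetes is not on the variety list. Only the statement that every irradiated patient may take part is contradicted outright.

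**The case for a change.** The best case for a change is that a sample-size basis belongs in the protocol, that this one asserts a basis and does not show it, and that correcting the text needs no extra patients. Under every significance level and power tried, the two stated rates allow only large yes/no effects to be detected. Even the ordinal analysis has only about 0.4 power at an odds ratio of 0.5 under the 10/70/20% split. An unlisted set of co-morbidities also leaves screeners to decide whether, for example, diabetes bars entry.

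Much of this stands as description. The calculation is not shown, the split is unexplained, and the power for moderate yes/no effects is low. What does not follow is that the plan makes a false statistical claim. The word sufficient is attached to data on varied patients, not to power or to subgroup tests, and the protocol plans no subgroup analysis. A detectable difference written in now would be back-fitted to a fixed 120 and would change no design feature. The co-morbidity list and the generalization sentence are separate matters of detail and tone.

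**Conclusion.** No change follows. The two sections do give different reasons for the size, and the sentence on open recruitment does conflict with the eligibility criteria. Both are faults of documentation. The criteria decide who enters, the arm sizes are fixed at 65 and 55, and neither fault touches the between-arm comparison.

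The sensitivity is modest: a fall from 90% to about 70%, or from 20% to about 3.5%, at an assumed two-sided 5% and 80% power (about 72.5% and 5% if one-sided). The protocol promises no better, and an analysis of grade or score does better than these figures. Equal allocation would gain 0.7%. Anyone reporting the trial can convey its precision through confidence intervals, and can limit conclusions to post-lumpectomy patients on this schedule, without amending the protocol.

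This conclusion rests on the protocol alone. The evaluation it refers to may be recorded elsewhere. It would change if the protocol claimed a stated power for a stated difference that 120 patients could not deliver.

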### **Eligibility:**

#### **Inclusion Criteria:**

1. Female patients aged at least 18 years with unilateral breast cancer following lumpectomy +/- chemotherapy.
2. Planned to receive 42.4 Gy whole breast irradiation +/- boost to tumor bed.
3. ECOG performance status 0-2.
4. Capable of giving written informed consent.
5. No co-morbidities known to affect radiotherapy reactions.
6. No co-existing acute or chronic skin disease.
7. No evidence of infection or inflammation of breast to be treated.

8. Not receiving chemotherapy during radiotherapy course. Biological therapy (e.g. Herceptin) or hormone therapy will be allowed during the study.

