**Exclusion Criteria:**

1. Chemotherapy within 4 weeks prior to planned start of radiation or chemotherapy planned during radiation.
2. Prior radiotherapy to the chest wall.
3. Collagen vascular disease.
4. Participation in other clinical study.

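### Does the unlisted co-morbidity criterion leave the eligibility of women with diabetes or high BMI open in a way that matters?

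*Protocol*

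**What the plan says.** Four parts of the protocol bear on the point.

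- **Inclusion Criteria, item 5**: "No co-morbidities known to affect radiotherapy reactions". No conditions are listed, and no one is named to decide.
- **Neighbouring criteria**: inclusion item 6 reads "No co-existing acute or chronic skin disease", and exclusion item 3 reads "Collagen vascular disease". None of the 12 criteria (8 inclusion, 4 exclusion) mentions diabetes or BMI.
- **Background**: "The severity of this acute reaction may link to different parameters, patient associated (BMI, diabetes". These are the only patient factors that the protocol itself links to severity.
- **Statistical Considerations**: the number of patients is justified by wanting "sufficient amount of data on large variety of patients (different age, BMI, skin color, origin, smokers/non-smokers etc". The same section adds that "Participation in this study will be offered and available to all radiation treated patient in the institute", and expects that "about 20% would require medical intervention due to grade 2-3 skin reactions".

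**The concern.** A criterion that removes patients for co-morbidities affecting the reaction, without naming them, sends the reader elsewhere for the list. The only candidates in the document are the two in the Background. Taken as the list, they would exclude women with diabetes and perhaps women with obesity. Yet the Statistical Considerations ask for varied BMI and describe an offer to everyone irradiated at the institute. One screener could turn away a woman with diabetes and another could enrol her, each pointing to the text.

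The factors in question are ones the protocol ties to severity, which is what the primary endpoint measures. The mix of women enrolled, the expected share needing intervention and the population to which the result applies could therefore depend on the reading. A statistical analysis plan would not repair this, because eligibility is settled in the protocol.

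**Working it through.** The protocol states no figure that depends on criterion 5, so there is none to reproduce. The check is mainly a comparison of texts.

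**BMI.** Criterion 5 concerns co-morbidities, and BMI is a measurement. The Statistical Considerations name it among the five kinds of variety sought: "large variety of patients (different age, BMI, skin color, origin, smokers/non-smokers etc". A conflict appears only if the Background sentence is taken as the list behind criterion 5, and nothing in the protocol makes it so. Even if obesity were barred, BMI would still vary among the remaining women. The variety would narrow, not vanish, and the stated reason for the sample size would survive.

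**The offer to all patients.** Taken literally, it would override nearly every criterion, including lumpectomy, the 42.4 Gy course and the bar on earlier chest-wall radiotherapy. The ordinary meaning is all patients who satisfy the eligibility lists. It is not a competing rule and does not admit a woman who fails criterion 5.

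**What criterion 5 adds.** It need not cover something beyond skin disease and collagen vascular disease. The protocol repeats itself elsewhere: inclusion item 8 and exclusion item 1 both rule out chemotherapy during radiation. Criterion 5 can be a general clause with specific instances set out beside it.

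**Diabetes.** This is a co-morbidity, and the Background mentions it. The Background speaks of a possible link, whereas criterion 5 asks for a known effect. No passage resolves the difference, so this gap is real.

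**How large could it be?** The document gives no prevalence or relative risk. Assume that a share *s* of otherwise eligible women, from 5% to 30%, has the disputed condition, with *RR* = 1.5 to 2 times the risk of a reaction needing intervention. Assume also that the 20% expected rate includes these women.

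- Places affected: 120 × 0.05 = 6, up to 120 × 0.30 = 36.
- If *q* is the rate without the condition, then 0.20 = *q*(1 − *s*) + *q* × *RR* × *s*, so *q* = 0.20 / (1 + *s*(*RR* − 1)).

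| *s* | *RR* | *q* | Expected events in 120 |
|---|---|---|---|
| none excluded | – | 0.200 | 24.0 |
| 0.05 | 1.5 | 0.20 / 1.025 = 0.195 | 23.4 |
| 0.10 | 2 | 0.20 / 1.10 = 0.182 | 21.8 |
| 0.30 | 2 | 0.20 / 1.30 = 0.154 | 18.5 |

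The spread comes wholly from the assumptions. The 20% is drawn from published data and earlier experience that may or may not have included such women. The protocol shows no calculation that uses it, and it justifies the number of patients by variety. Nothing displayed in the plan therefore changes between 24 and 18.5 events.

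**The case for a change.** The strongest reply concentrates on diabetes. It is undeniably a co-morbidity, the protocol itself names it in connection with the reaction under study, and the eligibility lists then pass over it. That makes the gap particular to this document, not a general wish for more detail. Appealing to clinical judgement is not a complete answer either, since the protocol gives that judgement to no one. Rewording one criterion and one sentence would cost little.

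The observation stands: the status of diabetes is not written down, and a reader of the results may want to know it. The consequence does not stand. That two screeners would decide differently is conjecture, because recruitment takes place in one radiotherapy unit and the protocol does not describe who screens. Inclusion items 6 and 7 are equally general and rely on the same judgement. The proposed rewording would only record a list whose content the investigator has to choose. Listing diabetes as an exclusion would also mean finding more candidates: under the assumed shares, 120 / 0.95 = 126.3, so 127 women, up to 120 / 0.70 = 171.4, so 172. No error in the analysis would be corrected in return.

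**Conclusion.** No change to the plan is called for. Of the apparent contradiction, one narrow point survives: criterion 5 does not say whether diabetes excludes a woman. The BMI conflict, the supposed clash with the offer to all patients and the effect on the sample-size rationale fall away once the passages are read together.

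The remaining gap is one that a single unit fills sensibly when it judges eligibility. Whichever way diabetes is handled, the decision comes before randomisation and the products are given in blinded packages, so the comparison between the 65 aloe vera and 55 hyaluronic acid patients stays sound. What can shift is the description of who was enrolled. By assumption, and not from the document, that concerns 6 to 36 of 120 places and an expected intervention rate between 15.4% and 20%.

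This conclusion rests on eligibility being judged without knowledge of the coming allocation. It does not say which women ought to be eligible, which is for the investigator. It also makes no claim about whether diabetes is recorded at baseline, because the data collection form is not shown.

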**Exclusion Criteria:**

1. Chemotherapy within 4 weeks prior to planned start of radiation or chemotherapy planned during radiation.
2. Prior radiotherapy to the chest wall.
3. Collagen vascular disease.
4. Participation in other clinical study.

**Statistical Considerations:**

Based on published data and previous experience we expect around 90% of patients to develop some degree of skin reaction and about 20% would require medical intervention due to grade 2-3 skin reactions. (Ben-David et al 2016, Fenig et al., Kodiyan et al. 2015, Olsen et al 2001).

The relative large number of patients in the study was chosen in order to be able to have sufficient amount of data on large variety of patients (different age, BMI, skin color, origin, smokers/non-smokers etc.). Participation in this study will be offered and available to all radiation treated patient in the institute, therefore large variety of patients are expected to participate in this study. As a result, the data that will be obtained in the study may be used by any irradiation institute in the world.

In addition to the weekly nurse/patient evaluation of skin toxicity (see appendix A), at the completion of the study the patient photographs will be evaluated blindly by a panel of 3 radiotherapy staff. The digital photo with the worst reaction of each patient will be scored.

**APPENDIX A (Translated from Hebrew to English)**
**Gelronate Study, Weekly Data Collection**
**Number in study** \_\_\_\_\_

**Filling date** \_\_\_\_\_

**Number of given fractions** \_\_\_\_\_ **Dose Gy** \_\_\_\_\_

**Skin condition**
**Status according to RTOG** \_\_\_\_\_ :

	0	1	2	3	4
Skin	No change over baseline	Follicular, faint or dull erythema/epilation/dry desquamation /decreased sweating	Tender or bright erythema, patchy moist desquamation /moderate edema	Confluent, moist desquamation other than skin folds, pitting edema	Ulceration, hemorrhage, necrosis

